## **12 Quality Assurance and Quality Control**

QA procedures include a study staff member at the DCSU verifying the exact lesion(s) of concern with the participant after the participant completes the enrollment questionnaire. DCSU study staff will double check the enrollment questionnaire for all missing information and ensure answers are filled out before the participant proceeds to the next step. All acquired images will be assessed for quality prior to acceptance and progression to Nevisense data acquisition. Study personnel will double check the Nevisense score prior to recording into the patient CRF.

QC procedures will be implemented beginning with the data entry system and an initial data QC check that will be run on the database once it is generated. Any missing data or data anomalies will be communicated to the site for clarification/resolution.

Following written SOPs, the monitors will verify that the clinical trial is conducted and data are generated, documented (recorded), and reported in compliance with the protocol, GCP, and the applicable regulatory requirements (e.g., Good Laboratory Practices (GLP), Good Manufacturing Practices (GMP)).

The investigational site will provide direct access of source data/documents, and reports for the purpose of inspection by local and regulatory authorities.

## **13 Ethics/Protection of Human Subjects**

### **13.1 Ethical Standard**

The investigator will ensure that this study is conducted in full conformity with Regulations for the Protection of Human Subjects of Research codified in 45 CFR Part 46, 21 CFR Part 50, 21 CFR Part 56, and/or the ICH E6.

### **13.2 Institutional Review Board**

The protocol, informed consent form(s), recruitment materials, and all participant materials will be submitted to the IRB for review and approval. Approval of both the protocol and the consent form must be obtained before any participant is enrolled. Any amendment to the protocol will require review and approval by the IRB before the changes are implemented to the study. All changes to the consent form will be IRB approved; a determination will be made regarding whether previously consented participants need to be re-consented.

#### **13.2.1 Telephone Pre-Screen:**

This study will have 2 consent processes: The first is the research team will speak with interested participants over the telephone and ask for verbal consent before asking some eligibility criteria-related questions.

Advertisements will list, and interested participants will be given the DCSU phone number to reach if they are interested in participating in the study. A phone pre-screen process with potential interested subjects will take place by phone when the participant calls the DCSU. The research team will ask for verbal consent prior to asking the pre-screen questions to determine if a potential participant is eligible to enroll in the study. The questions are in regards to the eligibility criteria which consist of age, pregnancy status, lesion location and history of prior biopsy of the lesion. If the individual is eligible for the study then they will be scheduled for a screening visit. If they are not eligible or decide not to participate, any information collected will be immediately destroyed. Informed Consent Process

#### **13.2.2 Consent/Assent and Other Informational Documents Provided to Participants**

Consent forms describing in detail the study procedures and risks are given to the participant and written documentation of informed consent is required prior to starting the intervention.

#### **13.2.3 Consent Procedures and Documentation**

Informed consent is a process that is initiated prior to the individual's agreeing to participate in the study and continues throughout the individual's study participation. Extensive discussion of risks and possible benefits of participation will be provided to the participants and their families. Consent forms will be IRB-approved and the participant will be asked to read and review the document. In a private room at the DCSU, the investigator will explain the research study to the participant and answer any questions that may arise. All participants will receive a verbal explanation in terms suited to their comprehension of the purposes, procedures, and potential risks of the study and of their rights as research participants. Participants will have the opportunity to carefully review the written consent form and ask questions prior to signing. The participants should have the opportunity to discuss the study with their surrogates or think about it prior to agreeing to participate. The participant will sign the informed consent document on the day of the consent discussion prior to any procedures being done specifically for the study. Alternatively, the participant may view and sign the consent form remotely through an electronic informed consent (e-consent) process prior to taking part in any study procedures. For the e-consent process, the discussion of consent will be conducted via phone after the telephone pre-screen. The participant will then receive a RedCap link to review and sign the electronic consent form. The RedCap consent document will include the same information contained within the paper informed consent document. In signing the consent form, subjects agree to comprehension of the nature of the study. The participants may withdraw consent at any time throughout the course of the trial. A copy of the signed informed consent document will be given to the participants for their records. The rights and welfare of the participants will be protected by emphasizing to them that the quality of their medical care will not be adversely affected if they decline to participate in this study.

A copy of the signed informed consent document will be stored in the subject's research record. The consent process, including the name of the individual obtaining consent, will be thoroughly documented in the subject's research record. Any alteration to the standard consent process (e.g. use of a translator, consent from a legally authorized representative, consent document presented orally, etc.) and the justification for such alteration will likewise be documented. A sample informed consent form is provided in the appendix of the protocol.

Capacity will be assessed if a subject is able to reiterate the risks and benefits of the study, articulate their decision and the rationale for his or her decision. Persons with diminished capacity are allowed to participate in the study as it is of minimal risk and offers the direct benefit of free cancer screening. Decisionally impaired adults will be asked to verbally state their decision and rationale to ensure comprehension during assent.

### **13.3 Participant and Data Confidentiality**

Information about study subjects will be kept confidential and managed according to the requirements of the Health Insurance Portability and Accountability Act of 1996 (HIPAA). Those regulations require a signed subject authorization informing the subject of the following:

- What protected health information (PHI) will be collected from subjects in this study
- Who will have access to that information and why
- Who will use or disclose that information
- The rights of a research subject to revoke their authorization for use of their PHI.

In the event that a subject revokes authorization to collect or use PHI, the investigator, by regulation, retains the ability to use all information collected prior to the revocation of subject authorization. For subjects that have revoked authorization to collect or use PHI, attempts should be made to obtain permission to collect at least vital status (i.e. that the subject is alive) at the end of their scheduled study period.

Participant confidentiality is strictly held in trust by the participating investigators, their staff, and their agents. This confidentiality is extended to cover testing of biological samples in addition to the clinical information relating to participants. Therefore, the study protocol, documentation, data, and all other information generated will be held in strict confidence.

Any clinical images captured using Epic Haiku or the study specific camera and include identifiable features (faces, full body images, tattoos, etc) will be stored directly in the patient's medical record as research note. The teledermatology team will have access to the patient's chart via an NYU EPIC MRN. Clinical images will not be stored on the device itself or any other platform. Identifiable images of participants will not be captured or stored in the DermLite Cam due to the standardized, constrained distance for clinical images required by this device.

Any clinical images captured using the Demetra that include identifiable features (faces, full body images, tattoos, etc) will be securely stored in the Demetra Cloud. The teledermatology team will have access to the patient's record via secure login access using username and password. Images are also stored on the Demetra device, which requires a user specific four-digit PIN code for operation.

The study monitor, representatives of the IRB or pharmaceutical company supplying study product may inspect all documents and records required to be maintained by the investigator, including but not limited to, medical records (office, clinic, or hospital) and pharmacy records for the participants in this study. The clinical study site will permit access to such records.

The study participant's contact information will be securely stored at the clinical site for internal use during the study. At the end of the study, all records will continue to be kept in a secure location for as long a period as dictated by local IRB and Institutional regulations.

Study participant research data, which is for purposes of statistical analysis and scientific reporting, will be transmitted to and stored at NYU Langone Medical Center. This will not include the participant's contact or identifying information. Rather, individual participants and their research data will be identified by a unique study identification number. The study data entry and study management systems used by clinical sites and by NYU Langone Medical Center research staff will be secured and password protected. At the end of the study, all study databases will be de-identified and archived at the NYU Langone Medical Center.

#### **13.3.1 Research Use of Stored Human Samples, Specimens, or Data**

There will not be storage of biological samples.

- Intended Use: Clinical and dermoscopic images, and Nevisense data may be used to study benign dermatological diagnoses and melanoma. No genetic testing will be performed.
- Storage: Access to the data (stored online) will be limited by password protection.
- Data will be kept in password-protected computers. Only investigators will have access to the samples and data.
- Tracking: not applicable.
- Disposition at the completion of the study: data described above will be maintained indefinitely. Study participants who request destruction of their data will be notified of compliance with such request and all supporting details will be maintained for tracking.

#### **13.4 Future Use of Stored Specimens**

Biological samples will not be obtained from the pathology laboratory and will not be used for future studies. Deidentified clinical and dermoscopic images may be used for future studies. Within the Informed Consent form, there is an optional

yes/no checkbox and place for an initial signature to provide this permission. These images could be used for research into the diagnosis of skin cancer and other conditions for which individuals with skin lesions are at increased risk, and to improve early detection. Any future studies with these images will be managed by the NYU IRB, just as this study is. One purpose of future studies would be to augment the strength of artificial intelligence diagnostics with a higher volume of images, particularly of the benign lesion category which currently is limited.

During the conduct of the study, an individual participant can choose to withdraw consent to have images stored for future research.

When the study is completed, access to study data and/or images will be provided through the DCSU.

## **14 Data Handling and Record Keeping**

### **14.1 Data Collection and Management Responsibilities**

Data collection is the responsibility of the clinical trial staff at the site under the supervision of the site PI. The investigator is responsible for ensuring the accuracy, completeness, legibility, and timeliness of the data reported.

All source documents should be completed in a neat, legible manner to ensure accurate interpretation of data. Black ink is required to ensure clarity of reproduced copies. When making changes or corrections, cross out the original entry with a single line, and initial and date the change. **DO NOT ERASE, OVERWRITE, OR USE CORRECTION FLUID OR TAPE ON THE ORIGINAL.** Time for submission of CRFs are within 48 hours of the visit. Paper source documents will be housed centrally at the DCSU.

Copies of the electronic CRF (eCRF) will be provided for use as source documents and maintained for recording data for each participant enrolled in the study. Data reported in the eCRF derived from paper source documents should be consistent with the paper source documents or the discrepancies should be explained and captured in a progress note and maintained in the participant's official electronic study record.

Clinical data (including AEs, prior or concomitant medications, and expected adverse reactions data) and clinical laboratory data will be entered into REDCap, a 21 CFR Part 11-compliant data capture system provided by NYULMC. The data system includes password protection and internal quality checks, such as automatic range checks, to identify data that appear inconsistent, incomplete, or inaccurate. Clinical data will be entered directly from the source documents.

Study staff at the DCSU will collect data as well as review data, trial materials, and reports. The study team will conduct interpretation of data, plans for analysis, review of tables and listings, and plans for reporting at locations within the NYU Department of Dermatology (e.g. office of the PI, conference rooms, etc.). After the study is completed, the de-identified, archived data will be stored in a dedicated folder in the NYU Department of Dermatology server allocation under the supervision of [name] (PI), for use by other researchers once relevant approvals are in place.

### **14.2 Study Records Retention**

Study documents will be retained for a minimum of 3 years after close-out or 5 years after final reporting/publication. However, images and associated meta-data will be retained indefinitely for potential use in future studies.

### **14.3 Clinical Safety Monitoring:**

[name] is responsible for overall clinical safety monitoring. As noted in Section 8.6, [name] is a Clinical Instructor in the Ronald O. Perelman Department of Dermatology. She is well qualified to serve as the Medical Monitor for this study. Clinical safety monitoring will consist of reviewing monthly summarized data of all the REDCAP CRFs, put together by the study's research coordinator or research associate. Research coordinator/associate will include a MoleCam software report AND/OR Demetra software report with images and locations for each lesion, and research coordinator/associate will confirm that all records have no missing data. The clinical safety monitoring report will also include frequency and nature of any adverse events, participant withdrawals, screen failures, number of enrolled participants, diagnoses, protocol deviations and the benign/malignant ratio. The literature suggests the typical benign: malignant ratio is about 29:1. The definition of non-inferior in the clinical trial setting is most often defined as within 50% unidirectionally from the endpoint of the control. In this case, a growth by 50% in this ratio becomes 44:1. Study stopping criteria will be when the teledermatology team reaches a benign: malignant ratio of 44:1, which will be a signal of unacceptably high added risk to the patient due to unnecessary skin biopsy procedure. If the Clinical Safety Monitor identifies a melanoma that was missed by the teledermatology team, and identified by the in person dermatologist, the Monitor will notify the PI and they will review the case. The clinical safety monitor will ensure all unanticipated problems involving risks to subjects or others are appropriately handled; interim safety reviews are performed; and the procedures for transmitting the results to the IRB are followed.

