### **2.4.2 Known Potential Benefits**

Study subjects will have up to three lesions of concern screened by a dermatologist for skin cancer at no cost. We anticipate participation in the study to offer immediate and long-term psychological benefit for subjects who have benign lesions and who receive reassurance. We estimate ~90% of subjects will have lesions not requiring biopsy and will receive such reassurance. Of the remaining subjects, it is likely that 8% will undergo a biopsy and receive a benign diagnosis, which will also be reassuring.

For subjects who are found to have malignant diagnoses (~2%), we anticipate substantial long-term physical, psychological, and economic benefit from this free screening service. These subjects would benefit from earlier detection of a malignancy that otherwise may have gone un-diagnosed. Inevitably the potential for early detection of melanoma or other skin cancers is associated with less costly treatment and less complicated care, decreased morbidity and mortality and overall improved outcomes.

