## 5 Study Enrollment and Withdrawal

### 5.1 Inclusion Criteria

In order to be eligible to participate in this study, an individual must meet all of the following criteria:

1. Be 18 years of age or older
2. Have 1-3 lesions for evaluation
3. Fluent in English language

Please note that the study will employ 2 diagnostic modalities: 1) clinical images (via photos of varying distances for each lesion uploaded to Epic EMR) and dermoscopic imaging via dermoscopic photos captured with the DermLite Cam and/or the Barco Demetra ; and 2) EIS as determined by the Nevisense device. We anticipate that subjects will present with skin lesions that do not meet the inclusion criteria for Nevisense (described in Section 6.1.4) but are suitable for clinical and dermoscopic imaging. For example, the original investigational studies with Nevisense 2.0 did not include large numbers of individuals from ages 18-30 or Fitzpatrick skin types 5-6, and thus safety and effectiveness has not been well established in these groups. While the FDA PMA has cautioned the use of Nevisense for diagnostic purposes in these patients, there is no contraindication to use in these populations. Any potential risk from using this device in these populations will be

mitigated by the fact that other diagnostic tools will be used on every lesion of concern (clinical images and dermoscopic images) and the fact that each concerning lesion will be assessed by an in-person dermatologist, the current gold standard for diagnostic evaluation.

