## 5.4 Strategies for Recruitment and Retention

Recruitment of study participants will be from advertisements in local newspapers (e.g., the New York Post, Daily News) and with social media virtual publications on Facebook and Instagram. The advertisement includes general information about the clinical trial and eligibility criteria, the Dermatology Clinical Studies Unit phone number, and a QR code that interested participants will be able to scan using their mobile devices. The QR code will link to the [clinicaltrials.med.nyu.edu](https://clinicaltrials.med.nyu.edu) page that states more detailed information about the investigative approach and the study team as well as an online form to contact the study team. We will also work with the Perlmutter Cancer Center to advertise the study to individuals on their lists. Please find the advertisements intended for publication as Supplement D and E. Additionally, participants will be recruited via the Research Match online platform, of which NYU is a participating institution. If needed, we will also use the Epic electronic health records to recruit patients from NYULMC. Participants meeting eligibility criteria after a pre-screening phone call (Section 7.3.1) will be directed to schedule an appointment with the DCSU for enrollment. The DCSU hosts a wide variety of dermatology studies and does not hold any particular stigma for participants. Our enrollment target is 500 subjects at a rate of 5 subjects per week. We anticipate pre-screening 650 participants to reach our enrollment goal.

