**10.4 Sample Size**

Number of subjects to recruit and screen is estimated to be 650 or fewer. Number of participants eligible is estimated to be 500 or fewer. Based on the previously mentioned Norwegian study, we anticipate a biopsy recommendation rate of 10% between the telemedicine and in-person evaluations. With each participant presenting with 1-3 lesions, an estimate of 1000 evaluated lesions (2 per participant on average) is possible. Assuming a biopsy recommendation 10% from this historical data, there will be likely 50 - 100 biopsies recommended and 450 - 900 lesions not recommended for biopsy.

We anticipate 2% of the sample will be lost to follow up based on historical data. Missing data is estimated at 4% based on those lost to follow up and technical error based on historical data. We anticipate 1% of participants to withdraw based on historical data. Participants who have formally withdrawn from the study will not be included in primary or secondary endpoint analysis, nor will they be included in the analysis datasets.

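### The 44:1 benign:malignant stop in section 14.3, with no minimum biopsy count and no rule for zero malignancies, cannot do its job at 50 to 100 biopsies

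*Combined protocol and SAP*

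**What the plan says.** Section 14.3 builds the limit in two steps. It starts from a benchmark, "The literature suggests the typical benign: malignant ratio is about 29:1", and allows 50% growth, by analogy with a non-inferiority margin. The rule follows: "Study stopping criteria will be when the teledermatology team reaches a benign: malignant ratio of 44:1". The stated purpose is to signal too many unnecessary biopsies. On timing, "Clinical safety monitoring will consist of reviewing monthly summarized data of all the REDCAP CRFs"; the monthly report includes diagnoses and the benign:malignant ratio.

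Other sections supply the expected numbers. Section 10.4 says "there will be likely 50 - 100 biopsies recommended and 450 - 900 lesions not recommended for biopsy". Section 5.4 says "Our enrollment target is 500 subjects at a rate of 5 subjects per week". On case mix, section 2.4.2 forecasts that "it is likely that 8% will undergo a biopsy and receive a benign diagnosis", and that about 2% of subjects will have a malignant diagnosis.

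Section 14.3 does not say how many biopsies must accrue before the ratio is read, what happens while the malignant count is zero, or how 29:1 relates to the forecast in 2.4.2. Section 8.5 (halting rules) covers only related grade 3 adverse events, and 10.3.7.1 (safety review) is marked not applicable.

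**The concern.** A stopping limit should be reached rarely when the study is performing acceptably and often when it is not. A ratio whose denominator is a handful of malignancies is very unstable: at 50 biopsies the whole decision turns on whether one or two are malignant. Monthly reading gives chance repeated opportunities to cross the limit.

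The benchmark adds a second difficulty. If 29:1 describes this population, the rule risks ending an acceptable pilot. If the forecast in 2.4.2 is nearer the truth, the limit lies so far away that the team could recommend many more unnecessary biopsies without reaching it. In both cases participants and investigators are relying on a safeguard that does not work as intended.

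**Working it through.** **The plan's own figures.** 29 × 1.5 = 43.5, rounded to 44: correct. 10% of 500 = 50 and 10% of 1,000 = 100: the biopsy range in 10.4 also reproduces.

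**What the forecast implies.** Per subject, 8% / 2% = 4:1. This is not a lesion ratio, but it bounds one. 2% of 500 = 10 subjects, hence at least 10 malignant lesions. If these are among the 50 to 100 biopsies, the ratio is at most (50 − 10)/10 = 4:1 or (100 − 10)/10 = 9:1.

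**Number of looks.** 500 / 5 per week = 100 weeks, or about 23 months, so 23 monthly looks.

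**Stopping probability.** Let N be the number of teledermatology-recommended biopsies with histology, spread evenly over time. Each is malignant independently with probability p = 1/(1 + ratio). Looks fall at round(N × k/23) biopsies, k = 1 to 23. The rule fires at the first look with benign ≥ 44 × malignant and at least one malignancy. An exact recursion on the malignant count gives the chance of ever firing. With no malignancy yet, the readings are:

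- (a) the rule cannot fire;
- (b) it fires once 44 benign have accrued.

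| True ratio | (a) N = 50 | (a) N = 100 | (b) N = 50 | (b) N = 100 |
|---|---|---|---|---|
| 4:1 | 0.04% | 0.03% | 0.04% | 0.03% |
| 8:1 | 2.7% | 2.4% | 3.0% | 2.5% |
| 9:1 | 4.3% | 4.0% | 4.8% | 4.1% |
| 29:1 | 36% | 54% | 54% | 58% |
| 43.5:1 | 40% | 68% | 72% | 78% |

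The rule is meant to separate 29:1 from 43.5:1. The difference in stopping probability is 4 points (a) or 18 points (b) at 50 biopsies, and 13 or 20 points at 100.

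**Why it is so coarse.** Two malignancies require 88 benign, impossible in 50 biopsies. Three require 132, impossible in 100. The rule is therefore out of reach after the second malignancy at N = 50 or the third at N = 100.

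**Can a better ratio rule be found at this size?** Separating 29:1 from 44:1 with one-sided 5% error and 80% power takes about 1,390 biopsies (exact binomial, single look).

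**Sensitivity, readings (a) and (b) together.**

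- 12 to 46 looks: 0.02-0.05% at 4:1; 36-60% at 29:1.
- Lesions in correlated pairs (assumed correlation 0.3, 100,000 simulated studies): 0.10-0.16% at 4:1; 32-60% at 29:1; 33-78% at 43.5:1.
- Team misses 5 of the 10 malignancies (assumed) with 100 biopsies: 95/5 = 19:1, still below 29:1; the rule fires in 32-33%.

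**The case against.** The strongest reply is that this is a pilot without hypothesis testing, under monthly review. The monitor sees the diagnoses as well as the ratio and can recommend on continuation (8.6), and 5.8 allows suspension followed by resumption. No ratio rule could separate 29:1 from 44:1 at this size, so the weakness lies partly in the study's size. The two harms are also alternatives: wrongful stopping matters only if 29:1 is about right, and weak protection only if the forecast is. All of this stands, and it limits the harm. It does not repair the rule. Section 14.3 gives a missed melanoma a case review but gives the ratio only a stop.

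Three stronger readings are tempting and should not be drawn.

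- **That the study would probably stop in its first months.** If zero malignancies is read literally as exceeding 44:1, the study stops at the first look in 64% (50 biopsies) or 41% (100) of cases at 4:1. These figures are just 0.8² and 0.8⁴, the chance that the first two or four biopsies are all benign. Two or four benign results do not naturally reach 44:1 and could not show the excess risk the rule is meant to detect. The reading is unlikely, though the text does not exclude it.
- **That 29:1 is wrong.** Nothing in the documents shows this. The forecast is per subject, covers all skin cancers and is not confined to the teledermatology team, whose own ratio may be higher because any one of three readers can trigger a biopsy. The benchmark is unreconciled, not refuted.
- **That the meaning of malignant is wholly open.** Sections 2.4.2 and 3.2 point to any skin cancer, and 14.3 says melanoma when it means melanoma. What is missing is a statement of this in the rule, and a benchmark known to be on the same footing.

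**Conclusion.** The concern holds. At 50 to 100 biopsies the rule stops a study running at its own typical ratio in roughly one third to three fifths of cases (36-58%), yet fires in at most 4.8% of cases anywhere in the forecast-derived range of 4:1 to 9:1. Which of these failures applies depends on the true ratio, which the documents do not settle.

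The figures rest on about 23 evenly spaced looks, independent biopsies, and all 50 to 100 biopsies being teledermatology-recommended with histology. Section 10.4 does not make clear whether that range covers both evaluators together or each one. If the team's own count stays below 44, the rule cannot fire at all under reading (a) or (b). The change should be made, but the existing monthly oversight means participants are not left unprotected meanwhile.

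**What to change.** Amend section 14.3 as follows.

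1. Make reaching 44:1 trigger a documented medical-monitor review with a recommendation on continuation, in place of a study stop.
2. Apply this only after at least 45 teledermatology-recommended biopsies with histology, because 44:1 with one malignancy needs 44 + 1 = 45. Refer zero malignancies at that point to the monitor as well.
3. State that malignant means any histologically confirmed skin cancer, consistent with 2.4.2 and 3.2, and put the benchmark on that same definition.

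The referral probabilities under this amendment equal those of reading (b). The minimum count removes any early chance stop but does not improve discrimination between 29:1 and 44:1. That is why a crossing should lead to judgement and not to a stop.

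The cost is a short amendment with no new data: histology and both evaluators' recommendations are already collected. The downside is less automatic protection, reliance on the monitor's judgement at small counts, and only the ordinary monthly review if fewer than 45 such biopsies accrue.
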